6.2.1.4 Metabolic and inflammatory biomarker studies

Blood and stool samples will be stored for metabolomics and biomarker studies. Both non-biased and targeted metabolomics profiling of the stool and blood will be performed at the West Coast Metabolomics Center at the University of California Davis. Filtered fecal water or plasma samples will be used for the mass spectrometry-based metabolomics profiling. The process of metabolite extraction will include internal standards and follow standard protocol. The resulting extract will be divided into a liquid chromatography fraction and a gas chromatography fraction.

6.2.1.5. Measurement of biomarkers of inflammation: Measurement of endotoxin, sCD14, hs-CRP, IL-6 and TNF- α will be performed at weeks 1, 2, 6, 10, 14, 17 and 20 of the study. Plasma LPS levels will be measured using a commercially-available kinetic chromogenic limulus amebocyte lysate assay kit (Lonza Walkersville, Walkersville, MD). High sensitivity sandwich ELISAs will be used to measure plasma sCD14, hs-CRP, IL-6, and TNF α . The samples will be stored at -80°C and assayed at the time of initial thawing to prevent degradation. All cytokine assays will be performed in duplicates. If funds are available, we will also measure IL-1 β , IL-2, IL-4, IL-17, IL-10, and IL-22.

6.2.1.6 Measurement of specific uremic toxins and bacterial metabolites in plasma:

Measurement of plasma p-cresol sulfate, indoxyl sulfate, TMAO and SCFA will be performed at 2, 4, 10, 14 and 20 weeks of the study. Plasma will be separated from whole blood samples collected in tubes containing EDTA as anti-coagulant. Extracted plasma will be frozen immediately after collection and store at -80°C until further use. The chromatographic separation of metabolites will be performed using either reverse phase separation or normal phase online with QQQ mass spectrometers (Agilent Technologies). For this, we will employ a combination of solvents including gradients at varying concentrations of ammonium acetate, methanol, acentonitrile adjusted for specific metabolites. Metabolites will be separated by controlled flow rates on either a Luna Phenyl Hexyl column (3um, 2x150mm, Phenominex), a Luna Amino (NH2) column (4um, 100A 2.1x150mm, Phenominex), or an orbax Eclipse XDB-C18 column (50 x 4.6 mm i.d.; 1.8 µm, Agilent Technologies, CA), while adjusting the temperature of the chamber. All the columns used in this study will be washed and reconditioned after every 50 injections.

6.2.1.7 Measurement of intestinal barrier dysfunction using plasma zonulin: Commensal gut microbes maintain functional integrity of gut by several mechanisms, including restoration of tight junction protein structure.(26) Dysbiotic gut microbiome may be an important contributor to intestinal barrier dysfunction by altering structure and localization of TJs. Zonulin. Human zonulin is a <47-kDa protein that increases intestinal permeability in small intestine by modulating intercellular TJs.(27) Circulating zonulin in serum is considered as a useful marker of intestinal permeability.(27) To measure the impact of Patiromer on intestinal permeability, we will measure circulating zonulin levels in our study participants at 1, 2, 6, 10, 14, 17 and 20 weeks of the study. Plasma zonulin levels will be measured using a commercially-available ELISA kit.

6.2.2 Other Specimen Analyses/Assays

6.2.2.1 Gut microbiota taxonomic analysis

The structure of the microbiota from frozen stool samples will be assessed by DNA sequencing and computational analysis. Stool samples will be collected for DNA extraction and shotgun metagenomic sequencing. DNA will be extracted using the MoBio PowerFecal DNA Isolation kit. Quantification and quality control of DNA samples will be run on a BioAnalyzer 2100. All samples will be run on an Illumina MiSeq or NextSeq, which will provide us with ~10 million reads per sample to allow for accurate characterization of the microbiome. Reads will be pre-processed using PRINSEQ-lite 0.20.4 (trimming reads and bases < 25 PHRED, removing exact duplicates, and reads with undetermined bases). We will construct a ‘target’ genome library containing all bacterial, fungal, and viral sequences from the Human Microbiome Project Reference Database (http://www.hmpdacc.org/reference_genomes/reference_genomes.php) using the PathoLib module from PathoScope 2.0. We will align the reads to these libraries using the Bowtie2 algorithm, and then filter any reads that also aligned to the human genome (hg19) as implemented in PathoMap (very-sensitive-local -k 100 --score-min L,20,1.0). We will then apply PathoScope 2.0, specifically the PathoID module, to obtain accurate read counts for downstream analysis, including mapping against both a microbial database to identify species/strains and calculate relative abundances to determine the impact of Patriomer on the gut microbiome. Analyses, including testing of abundance of target species in treated patients and tests of correlations of changes in abundance with changes in metabolomics will be performed in R and Bioconductor using packages xlsx, gtools, CHNOSZ, plyr, ggplot2, reshape2, gplots, Phyloseq, and DESeq2.

6.3 Study Schedule

6.3.1 Schedule of Events Table

Table 1: Study procedures and time-line

Weeks	Intervention 2 to 14 weeks														17	20
	0	1	2	3	4	5	6	7	8	9	10	11	12	13	14	
Physical examination	•															
Serum/Urine Pregnancy Test ¹	•															
Serum K				•		•		•	•	•	•	•	•	•		
Serum Mg++ Test			•				•								•	•
Comprehensive metabolic panel	•		•		•						•				•	•
CBC	•		•		•						•				•	•
Study medication dispensing			•				•				•					
Blood sample collection		•	•	•	•		•			•				•	•	•
Endotoxin, sCD14, Zonulin and inflammatory biomarkers*†		•	•				•			•				•	•	•
Stool sample collection		•	•	•	•		•			•				•	•	•
Microbiome studies (Metagenomics)†		•	•		•		•			•				•	•	•
Metabolomics†			•		•					•				•		•
Gastrointestinal health assessment survey		•							•					•		•
Dietary assessment using food frequency questionnaire		•							•							•
Phosphorous and PTH‡	•															
Dialysis prescription and medication reconciliation‡	•	•	•				•			•				•	•	•

† A purposeful approach to analyzing the stored blood and stool samples will be used.

‡ Extracted from dialysis unit medical record periodically when new results are available

*hs-CRP, IL-6, and TNF- α

¹ For women of child bearing potential

The following will be collected monthly from the dialysis unit:

- Routine labs from dialysis unit including comprehensive metabolic panel, Mg++, hematological parameters, iron profile and dialysis adequacy
- Medication use including EPO, iron, proton pump inhibitor, phosphate binders, use of other potassium lowering agents, and vitamin D
- Data about infection, antibiotic use and adverse reaction to study drug will be collected by the study coordinator from personal interview with the patient, dialysis unit and inpatient/outpatient records

6.3.2 Screening Visit (Week 0)

Patients who appear eligible based on pre-screening will be approached in person to determine interest in participation and confirm eligibility. Study personnel will discuss the study goals and procedures with the potential participant in detail. Patients should have an understanding of the importance of providing frequent stool samples and what the process entails. If the patient agrees to participate in the study, study personnel will review and assess understanding of the entire informed consent form prior to obtaining written informed consent from the participant. The consenting process will be performed by a qualified investigator or study site designee. Informed consent will be obtained and documented before any study procedures are performed.

The following activities may take place over one or two visits.

- Determination of eligibility
- Informed consent process
- Collection of baseline data including demographics, medical history, and medication use including recent and current use of prescription products, over-the-counter products, herbal supplements, vitamins, and prebiotic and probiotic use in any form. In addition, medical records from the clinic facility will be reviewed to capture any non-reported data on recent medication use.

- Blood draw (13mL): Blood samples collected at Screening will be tested for the CMP, CBC, phosphorous and PTH.
- Serum pregnancy test for women of childbearing potential and tested at local lab.
- Instruction in stool sample collection and storage
- Instruct enrolled participants **not to change their dietary patterns**, if possible, during the study

6.3.3 Assigning a Participant ID

After the participant has signed the informed consent form, assign a unique 5-digit Participant Identification number (PID). Each participant should be assigned the next available PID.

6.3.4 Stool Sample Collection

Subjects will be provided with detailed instructions on how to collect and store their stool samples. Subjects will be instructed to collect samples from bowel movements at weeks 1, 2, 3, 4, 6, 10, 14, 17, and 20.

7 Evaluations and Follow Up

Participants will have in-person study visits at Weeks 1, 2, 3, 4, 6, 10, 14, 17 and 20. At each study visit, participants will be asked about emergency room visits, hospital admissions or any significant clinical events that occurred since the last visit. RCs will have weekly contact with participants to query them on antibiotic use in the previous week and medical records will be reviewed for blood potassium levels and antibiotics administered.

Dietary assessment using the Block Food Frequency Questionnaire (<https://nutritionquest.com>) will be administered at Baseline (W1), W8 and W20.

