2.2 Study Endpoints

2.2.1 Primary Endpoint

- For Specific Aim 1, the primary safety end point is adverse events during the 12 weeks of intervention.
- For Specific Aim 2, the primary efficacy end points will be change in microbiome, metabolome and markers of inflammation.

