4 STUDY PRODUCTS

4.1 Safe Use of Study Agent

Patiromer is an FDA-approved orally administered drug used for the treatment of hyperkalemia. It is a non-absorbed polymer that binds potassium throughout the gastrointestinal tract and leads to lowering serum potassium levels (1). Prior Patiromer clinical trials have demonstrated the drug's utility in treating hyperkalemia in patients with diabetic kidney disease (1; 2). Adverse events and other safety data will be obtained at each visit. The most commonly reported treatment related adverse events have been hypomagnesemia (7.2%), constipation (4.6%), and diarrhea (2.7%).

This study incorporates several design elements to minimize adverse events related to the study agent including:

- Eligibility criteria that exclude individuals with normal or low blood potassium levels. Only ESRD patients with hyperkalemia ($K>5.0$ mEQ/L) will be enrolled
- A maximum daily Patiromer dose of 16.8 g once daily
- Frequent monitoring of gastrointestinal symptoms
- Regular monitoring of concomitant medications and antibiotic use
- Pre-dialysis serum potassium will be monitored at regular intervals. Appropriate adjustment in dialysate potassium will be made to avoid hypokalemia.
- Follow-up of serum magnesium levels

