5.2 Collecting Adverse Event Information

The Investigator and research team is obligated to monitor participants so that their participation in the clinical trial is as safe as possible.

The center staff will collect adverse event data at each study visit by checking several different sources of information by:

- asking participants directly
- evaluating medical record information
- reviewing all laboratory values
- examining reports generated by the data management system based on data entered into logs and forms

AE information may also be reported between scheduled study visits via regular contacts if the participant reports health related problems or concerns. The study period during which adverse events must be reported is defined as the period from initiation of the study procedures to the end of the treatment follow-up. In other words, AE documentation should begin when the patient signs the informed consent form.

Encourage participants to contact the investigator after the conclusion of the trial if subsequent medical events occur which the participant, or the participant's physician, believes may be related to participation in the research study.

Other medical information

A participant may report that he or she had a medical test or procedure. If so, inquire as to why this was done as it may reveal pertinent information about a medical condition or diagnosis. In addition, if a participant reports starting a new medication, it may also indicate a new diagnosis or a change in a pre-existing medical condition that should be discussed and documented on the AE form.

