7.1 Pre-Treatment Observation Phase [Week 1 and 2]

The following activities will be performed during in-person visits at weeks 1 and/or 2:

- Study Visit Assessment
- Blood Specimen Collection
- Stool Sample Collection
- Antibiotic use review
- Study medication dispensing (Week 2 only)
- Review of adverse events
- Dietary assessment using food frequency questionnaire (Week 1 only)
- Gastrointestinal symptom assessment questionnaire (Week 1 only)
- Serum Mg++ (week 2 only)

Treatment Phase [Weeks 3-14]

The following activities will be completed during in-person visits at weeks 3, 4, 6, 10 and 14:

- Study Visit Assessment
- Review of information on clinical events and current use of medications
- Blood K+ levels (weeks 3, 5, 7, 8, 9, 11, 12, and 13)

- Serum Mg++ (weeks 2, 6, 14 and 17)
- Blood Specimen Collection
- Stool Sample Collection
- Gastrointestinal symptom assessment questionnaire administration (Weeks 8 and 14)
- Review of adverse events
- Study medication dispensing (Weeks 2, 6 and 10 only)

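### In study weeks 7 to 14, adverse events (the primary safety endpoint) are actively asked about only about every 4 weeks, apart from a GI questionnaire at week 8; the existing weekly contact could carry the question

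*Combined protocol and SAP*

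**What the plan says.** Section 2.2.1 states that "the primary safety end point is adverse events during the 12 weeks of intervention". Section 5.1 defines an adverse event broadly, so a mild symptom counts whether or not it is related to the drug.

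On collection, section 5.2 says "The center staff will collect adverse event data at each study visit", using direct questions, medical records, laboratory values and data-system reports. Between visits the rule is passive: "AE information may also be reported between scheduled study visits via regular contacts if the participant reports health related problems or concerns".

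Section 7 sets the timetable: "Participants will have in-person study visits at Weeks 1, 2, 3, 4, 6, 10, 14, 17 and 20". Section 7.1 lists adverse-event review in each phase. For the pre-drug phase: "The following activities will be performed during in-person visits at weeks 1 and/or 2". For treatment: "The following activities will be completed during in-person visits at weeks 3, 4, 6, 10 and 14". The same list places a GI symptom questionnaire at weeks 8 and 14.

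Section 7 also provides that "RCs will have weekly contact with participants to query them on antibiotic use in the previous week", with record review for potassium and antibiotics. It lists no symptom question for that contact.

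Two other provisions bear on the point. The notes under Table 1 (section 6.3.1) put a coordinator interview about reactions to the study drug among the items collected monthly. Section 4.1 names this safeguard: "Frequent monitoring of gastrointestinal symptoms".

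**The concern.** Events that leave no record elsewhere depend on the participant's memory at the next active question. A few days of constipation, nausea or headache early in a 4-week gap may not be mentioned at the end of it. The spacing is widest in the last 8 treatment weeks, which is most of the period over which the endpoint is counted.

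The trial is small, so individual events carry weight. One participant in 25 is 4 percentage points. As a rough guide only, the treatment-related rates in section 4.1 applied to 25 participants give 25 x 4.6% = 1.2 with constipation and 25 x 2.7% = 0.7 with diarrhea. A single unrecorded case would visibly change such a table.

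The study team already speaks to each participant every week, so the opportunity to ask exists and is not used for the primary safety endpoint.

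**Working it through.** The plan gives no adverse-event rate, precision target or recall figure for this endpoint, so there is no stated number to reproduce. The check is of the schedule, followed by a sensitivity range.

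**Intervals between active questions** (sections 7 and 7.1; drug starts at week 2)

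- Pre-drug, weeks 0, 1, 2: gaps 1, 1.
- On drug, visits only, weeks 2, 3, 4, 6, 10, 14: gaps 1, 1, 2, 4, 4 (sum 12). Share in 4-week gaps = 8/12 = 67%.
- On drug, GI symptoms, adding the week-8 questionnaire: gaps 1, 1, 2, 2, 2, 4. Share in a 4-week gap = 4/12 = 33%.
- Post-drug, weeks 14, 17, 20: gaps 3, 3.

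The monthly coordinator interview does not shorten a 4-week gap.

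**Mean time from event to question**, with events uniform in time = sum(L²) / (2 x sum(L)), where L is the gap in weeks:

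- Pre-drug: 2/4 = 0.50 weeks.
- On drug, visits only: (1+1+4+16+16)/24 = 1.58 weeks.
- On drug, GI with week 8: (1+1+4+4+4+16)/24 = 1.25 weeks.
- Post-drug: 18/12 = 1.50 weeks.

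**Sensitivity to recall loss.** The loss rate r is an assumption; the documents give none. Capture over a gap L is (1 - exp(-rL))/(rL), averaged over weeks.

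| r per week | L=1 | L=2 | L=3 | L=4 |
|---|---|---|---|---|
| 0.1 | 0.952 | 0.906 | 0.864 | 0.824 |
| 0.2 | 0.906 | 0.824 | 0.752 | 0.688 |

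- On drug, visits only, r = 0.1: (2 x 0.952 + 2 x 0.906 + 8 x 0.824)/12 = 0.859; ratio to pre-drug 0.859/0.952 = 0.90.
- On drug, visits only, r = 0.2: (2 x 0.906 + 2 x 0.824 + 8 x 0.688)/12 = 0.747; ratio 0.747/0.906 = 0.82.
- GI with week 8, r = 0.1: (2 x 0.952 + 6 x 0.906 + 4 x 0.824)/12 = 0.886; ratio 0.93.
- GI with week 8, r = 0.2: (2 x 0.906 + 6 x 0.824 + 4 x 0.688)/12 = 0.793; ratio 0.87.
- On drug against post-drug: 0.859/0.864 and 0.747/0.752, both 0.99.
- At r = 0 every ratio is 1.00.

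Reading the loss as a fixed 10% or 20% of events per week changes little: 0.90 and 0.81 overall, 0.93 and 0.86 for GI symptoms.

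**With a weekly question**, every on-drug gap is 1 week, the mean lag falls from 1.58 to 0.50 weeks, and the ratio to pre-drug is 1.00 at any loss rate.

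**The case against.** The schedule has a sensible shape. Visits are weekly at drug start and around the planned dose increase (weeks 3 and 4), as frequent as before drug, and thin out later. Capture is also not recall alone: section 5.2 requires records and laboratory values to be checked at each visit, and the notes under Table 1 add dialysis-unit and inpatient/outpatient records. The weekly contact is open to adverse events if the participant raises one. The week-8 questionnaire falls in the middle of the week 6 to 10 gap and covers the symptoms most expected with this drug. Section 4.2.1 already confirms adherence through regular communication and a count of doses.

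All of that stands, and it limits the point to mild events that leave no record. It does not remove it. Non-GI symptoms gain nothing from the GI questionnaire, the documents do not say that its answers are entered as adverse events, and weeks 11 to 14 remain one 4-week gap for every symptom.

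A reader might infer that adverse events are sought only at visits, or that the weekly contact excludes them. Neither is so, given the questionnaire, the monthly interview and the between-visit rule. A reader might also infer a biased comparison of on-drug with drug-free weeks. The plan defines no such comparison, and against the 6 post-drug weeks the modelled capture is almost equal (0.99). Only the 2 pre-drug weeks have clearly tighter questioning.

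**Conclusion.** The point holds as a cheap improvement to collection of the primary safety endpoint, not as an error in the plan. Active questioning is about every 4 weeks in study weeks 7 to 14, apart from the week-8 GI questionnaire. Mild, short-lived symptoms may be missed: chiefly non-GI ones across those weeks and GI ones in weeks 9 to 14.

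It would go too far to state that on-drug events are under-captured by a given amount. The range of 1.00 to about 0.82 overall (1.00 to about 0.87 for GI symptoms, if week-8 answers become adverse-event entries) rests wholly on an assumed loss of 0 to 20% per week. The model also treats each event as over at onset and ignores every source but recall. Symptoms still present at a visit need no recall, so for a given loss rate the true shortfall is likely to be smaller. Serious, chart-recorded and laboratory events are little affected.

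**What to change.** In section 7, add a short fixed question set to the existing weekly contact, worded identically in every week from 1 to 20: any new or worsened symptom (with the common GI symptoms named), and any emergency visit or admission, with onset and stop dates entered on the adverse-event form. Amend section 5.2 so that adverse-event data are collected at each visit and at each weekly contact. State whether GI questionnaire answers are entered as adverse events. A missed-dose question is optional, since section 4.2.1 already provides for adherence checks.

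The cost is a few more questions per contact and more adverse-event entries, with no added visits or samples. The documents do not describe how the weekly contact is staffed, so the extra time should be confirmed. The reported rate of mild events will probably rise somewhat, and the report should say that events were actively solicited each week.

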7.1 Pre-Treatment Observation Phase [Week 1 and 2]

The following activities will be performed during in-person visits at weeks 1 and/or 2:

- Study Visit Assessment
- Blood Specimen Collection
- Stool Sample Collection
- Antibiotic use review
- Study medication dispensing (Week 2 only)
- Review of adverse events
- Dietary assessment using food frequency questionnaire (Week 1 only)
- Gastrointestinal symptom assessment questionnaire (Week 1 only)
- Serum Mg++ (week 2 only)

Treatment Phase [Weeks 3-14]

The following activities will be completed during in-person visits at weeks 3, 4, 6, 10 and 14:

- Study Visit Assessment
- Review of information on clinical events and current use of medications
- Blood K+ levels (weeks 3, 5, 7, 8, 9, 11, 12, and 13)

- Serum Mg++ (weeks 2, 6, 14 and 17)
- Blood Specimen Collection
- Stool Sample Collection
- Gastrointestinal symptom assessment questionnaire administration (Weeks 8 and 14)
- Review of adverse events
- Study medication dispensing (Weeks 2, 6 and 10 only)

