4.2 Study Agent Dose Adjustments

4.2.1 Protocolized Dosing of Study Agent

Participants will orally self-administer Patiromer at a dose of 8.4 gram, once daily and observed for a week, during which serum potassium and gastrointestinal symptoms will be evaluated. If tolerated and in the absence of hypokalemia (serum potassium less than 4 meq/L), the dose will be up-titrated to 16.8 g once daily. Participants will remain on the 16.8 g daily dosage for another 11 weeks, for a total of 12 weeks of treatment. Study agent kits will contain 4 weeks'

worth of doses, and will be distributed three times during the course of the study. Pharmacoadherence will be ensured and confirmed through frequent communications and pill count.

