6 STUDY PROCEDURES AND SCHEDULE

6.1 Study Procedures/Evaluations

6.1.1 Study Specific Assessments and Procedures

This section describes the study specific assessments and procedures that will be conducted. Results from study specific procedures (e.g., laboratory evaluations or questionnaire results) will not be provided to subjects, unless the results are necessary in order to effectively communicate follow-up care for any adverse events that may occur as a result of participating in the study.

[figure not shown]

Figure 1. Sample collection. Stool and blood samples will be collected at weeks 1, 2, 3, 4, 6, 10, 14, 17 and 20 of the study. We will obtain information regarding dietary pattern and gastrointestinal health. Adverse events related to study drugs, and clinical events will also be collected. Patients will be requested to complete gastrointestinal (GI) health assessment survey at baseline, during treatment, and during post-treatment phase. Detailed information about infection and type of antibiotic used (if any) will be collected.

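### The study-specific magnesium schedule guarantees no on-drug value before the dose is doubled and leaves 8 weeks between weeks 6 and 14; the monthly unit labs that narrow this gap are not tied to the dose step

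*Combined protocol and SAP*

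**What the plan says.** **Dosing.** The pre-treatment list in section 7.1 has "Study medication dispensing (Week 2 only", and Table 1 (section 6.3.1) heads the treatment columns "Intervention 2 to 14 weeks". Section 4.2.1 starts at 8.4 g once daily for a week, "during which serum potassium and gastrointestinal symptoms will be evaluated". The dose then goes to 16.8 g for 11 further weeks if the drug is tolerated and potassium is not below 4 mEq/L. Magnesium is not named.

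**Study-specific magnesium.** The pre-treatment list has "Serum Mg++ (week 2 only". The treatment-phase list has "Serum Mg++ (weeks 2, 6, 14 and 17". The magnesium row of Table 1 gives the same four weeks.

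**Known risk.** Section 4.1 lists hypomagnesemia (7.2%) ahead of constipation (4.6%) and diarrhea (2.7%). Among the design elements meant to limit adverse events it lists "Follow-up of serum magnesium levels", without weeks or limits.

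**Monthly labs.** The notes under Table 1 plan monthly collection of routine dialysis-unit results and name magnesium separately from the metabolic panel.

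**Endpoint and capture.** Adverse events over the 12 treatment weeks are the primary safety endpoint (section 2.2.1). An abnormal laboratory finding is an adverse event (section 5.1). Staff collect events at each visit from several sources, including the medical record and all laboratory values (section 5.2).

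**The concern.** Low magnesium can go unnoticed unless it is measured, so how often this event is recorded depends on when magnesium is tested. Week 2 is a baseline value. Of the remaining study-specific values, week 6 falls within dosing, week 14 marks its end, and week 17 follows it. The step from 8.4 g to 16.8 g comes before any of them.

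Two things are at stake. The first is safety information around the dose step, where section 4.1 relies on magnesium follow-up but section 4.2.1 does not mention it. The second is how evenly the primary safety endpoint captures the first-listed treatment-related event. By comparison, the treatment-phase list schedules potassium at eight weeks (3, 5, 7, 8, 9, 11, 12 and 13) in addition to the metabolic panels.

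**Working it through.** The protocol gives no figure of its own to reproduce here, so the check is a count against the schedule plus a timing calculation.

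**1. Timeline** (sections 4.2.1, 6.3.1 and 7.1)
- Dose ratio: 16.8 / 8.4 = 2.0.
- Treatment: 1 + 11 = 12 weeks, from week 2 to week 14.
- Dose step: 2 + 1 = week 3.

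**2. Study-specific magnesium, weeks 2, 6, 14 and 17**
- After the first dose and up to week 3: none.
- After the first dose and strictly before week 14: one (week 6). Counting the end-of-treatment value: two (weeks 6 and 14).
- Week 6 is 6 − 2 = 4 weeks after the first dose and 6 − 3 = 3 weeks after the step.
- Gaps between values: 6 − 2 = 4, 14 − 6 = 8 and 17 − 14 = 3 weeks.

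**3. What the monthly unit labs add**

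The protocol says monthly and no more. I assume an interval of 28, 30 or 31 days and a start that is random relative to the first dose. Dosing lasts 12 × 7 = 84 days, and the window before the step is 7 days.

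| Interval (days) | Mean on-drug values, 84 / interval | Range | Share with a value before the step, 7 / interval | Share without | Patients of 25 with a value |
|---|---|---|---|---|---|
| 28 | 3.0 | 3 | 25.0% | 75.0% | 6.3 |
| 30 | 2.8 | 2–3 | 23.3% | 76.7% | 5.8 |
| 31 | 2.7 | 2–3 | 22.6% | 77.4% | 5.6 |

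With weeks 6 and 14, a patient would have about 4 to 5 on-treatment values. About 6 of 25 would have one in the week before the step, and about 19 would not.

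The random start matters. If unit draws instead fell at the week-2 visit and every 4 weeks after it, they would come at weeks 2, 6, 10 and 14. Only week 10 would then be a new time point, and no patient would have a unit value between the first dose and the step.

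**4. Context only**

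If 7.2% applied to this cohort and patients were independent:
- Expected cases: 25 × 0.072 = 1.8.
- Chance of at least one: 1 − 0.928^25 = 0.85.

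These describe how often the event might occur. They do not measure cases missed.

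**5. Feasibility**

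The Figure 1 legend says "Stool and blood samples will be collected at weeks 1, 2, 3, 4, 6, 10, 14, 17 and 20 of the study". Weeks 3, 4 and 10 are among these. Clinical chemistry is already planned at all three: potassium at week 3 (treatment-phase list) and the metabolic panel at weeks 4 and 10 (section 6.2.1.3).

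**The case against.** The strongest answer is that the monthly unit labs already cover magnesium. A reader of the magnesium row alone might infer that only one value exists before dosing ends, or that the hypomagnesemia rate rests on two values. The documents do not support either reading. Monthly magnesium collection is itself in the protocol, and section 5.2 brings all laboratory values into adverse event collection. Monthly values would normally interrupt the 8-week gap. This part of the objection stands.

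It is also fair to say that a unit draw may happen to fall in the first week on drug. The accurate statement is that no value is guaranteed there, not that none will exist.

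A reader might also infer that a definite share of cases would be missed. Nothing supports a figure. An episode would have to begin after week 6, resolve by week 14 and escape the monthly labs as well, and no section describes that course. Section 4.1 does not say in what population, over what period or with what sampling the 7.2% arose.

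Finally, sections 4.1 and 4.2.1 do not flatly contradict each other. Section 4.1 promises follow-up without dates, the schedule delivers some, and the tolerability condition in section 4.2.1 is not expressly limited to gastrointestinal symptoms.

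What the objection does not answer is the timing at the dose step. No section ties the monthly values to it or says that they are reviewed before it. The weekly record review in section 7 names potassium and antibiotics, not magnesium. Section 6.1.2 says that no standard-of-care procedures apply to the study, which sits awkwardly with collecting routine unit labs.

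**Conclusion.** The point holds in a limited form. The study-specific schedule has no guaranteed on-drug magnesium value before the dose is doubled at week 3, and 8 weeks separate its two on-treatment values. Monthly unit labs probably add 2 to 3 on-drug values per patient, so mid-treatment detection is better than the magnesium row suggests. They leave about 75% to 77% of patients without a value in the week before the step.

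The week counts come directly from the protocol. The monthly counts and percentages rest on my assumptions of a 28- to 31-day interval and random timing, and they would shift if unit draws were aligned with study visits. The 1.8 expected cases and the 85% chance of at least one are context and assume that 7.2% carries over to this hemodialysis population.

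This is a cheap improvement to safety measurement and to capture of the primary safety endpoint. It does not show that the endpoint is invalid or that the dosing plan is wrong.

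**What to change.** - In Table 1 and the treatment-phase list of section 7.1, add serum magnesium to the blood already drawn at weeks 3, 4 and 10. This gives protocol-timed on-drug values at the week of the dose step, one week later and mid-treatment, and splits the 8-week gap into two of 4 weeks.
- In section 5.2 or the notes under Table 1, state that monthly unit magnesium values count toward adverse event ascertainment, and who reviews them and when.
- Reconcile sections 4.1, 4.2.1, 6.1.2, 6.3.1 and 7.1 on how magnesium follow-up relates to treatment, and on whether routine unit labs are part of the study. Whether and how a magnesium result affects dosing is for the investigator and sponsor to decide.

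**Cost:** 3 assays × 25 patients = 75 assays, with no new visits or draws, plus short text edits. More frequent testing may raise the observed hypomagnesemia rate, which should be kept in mind when it is compared with the 7.2% in section 4.1.
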